## 9.2 Safety Assessments

Safety assessments will be conducted for all subjects at the screening visit (upon signing of the ICF) and at every subsequent visit.

### 9.2.1 Subject Assessment of Pain

At Visit 2, 2b (if applicable), and Visit 4, 4b (if applicable), after the treatment session (once illumination in daylight is terminated), the subject will assess the maximal pain felt during daylight exposure. The subject will complete this assessment for all DL-PDT exposures, both complete and incomplete. The pain sensation will be assessed on an 11-point Numerical Rating Scale (NRS), where 0 is no pain at all and 10 is extreme pain as shown in [Table 8](#). The site personnel will collect and report the subject's self-assessment of pain in the Procedure Log. In the event that a subject requires an intervention for pain such as medication, it will then be recorded as an AE in the eCRF.

**Table 8: Scale for Subject Self-Assessment of Pain**

| 0                        | 1                        | 2                        | 3                        | 4                        | 5                        | 6                        | 7                        | 8                        | 9                        | 10                       |
|--------------------------|--------------------------|--------------------------|--------------------------|--------------------------|--------------------------|--------------------------|--------------------------|--------------------------|--------------------------|--------------------------|
|  |  |  |  |  |  |  |  |  |  |  |
| No
pain
at all     |                          |                          |                          |                          |                          |                          |                          |                          |                          | Extreme
pain          |

### 9.2.2 Safety Visit Question

At Visits 3 and 5, particular attention is paid to AEs and events which can be sequelae of treatment.

The Investigator will answer the following question at each of Visit 3 and Visit 5:

Does the subject exhibit signs and symptoms of possible contact sensitization?

|                              |                             |
|------------------------------|-----------------------------|
|  YES |  NO |
|------------------------------|-----------------------------|

If YES, then see [Sections 9.2.4.2](#) and [9.4.4](#) of this protocol.

If the Investigator recognizes signs and symptoms of possible contact sensitization at other visits during the study, he/she should report these as an Adverse Event of Special Interest proceed to those sections of the protocol.

### 9.2.3 Clinical Assessment of the Subject's Skin Aspect

At Visit 6, for each lesion that has responded completely (see [Table 7](#)), the Investigator will assess the subject's skin aspect on the following signs: scarring, atrophy, induration, redness or change in pigmentation. (see [Table 9](#))

The clinical assessment of skin aspect will be graded as:

**Table 9: Scale for Clinical Assessment of Subject's Skin Aspect**

|           |   |  |
|-----------|---|--|
| Excellent | 3 | No scarring, atrophy or induration, and no or slight occurrence of redness or change in pigmentation compared to adjacent skin |
| Good      | 2 | No scarring, atrophy or induration, but moderate redness or change in pigmentation compared to adjacent skin                   |
| Fair      | 1 | Slight to moderate occurrence of scarring, atrophy or induration   |
| Poor      | 0 | Extensive occurrence of scarring, atrophy or induration  |

In the event of the score of 2 or less for the clinical assessment of subject's skin aspect, it will be recorded as an AE in the eCRF.

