| Subject satisfaction questionnaire  |   |   |  |  |   |   |  | X |   | X d |
| Safety visit question   |   |   |  |  |   | X |  |   | X |                |
| Adverse Events e   | X | X |  |  | X | X |  | X | X | X              |
| Concomitant Therapies/Procedures d   |   | X |  |  | X | X |  | X | X | X              |
| Subjects with Complete Response evaluation and IC for continuation into long-term follow-up study |   |   |  |  |   |   |  |   |   | X              |
| Exit Form f  |   |   |  |  |   |   |  |   |   | X              |

- a) Visits 2 and 4 may be delayed for up to 2 weeks in case of unsuitable weather conditions at randomization/treatment outset. These postponements will be automatically added to the time of scheduled Visits 5 and 6
- b) If subjects experience rain during the 2 hours of daylight exposure of either DL-PDT visit, they will be instructed to go indoors at the investigative site and the study drug will be washed off. The treatment will be considered incomplete and should be repeated at a minimum interval of 2 weeks, with a maximum interval of 4 weeks. There will be only one attempt at retreatment of an incomplete treatment. These visits will be Visits 2b and 4b. If the attempt at retreatment is also incomplete, the subject will continue in the study. Likewise these repeat visits will be added to the time of scheduled Visits 5 and 6.
- c) Only for females of childbearing potential, urine at Visits 1, 2, 2b (if applicable), 4, 4b (if applicable) and 6
- d) Should be performed earlier if subject discontinues before Visit 6
- e) Adverse Events have to be collected from the time of the Informed Consent signature
- f) Exit form should be completed after subject data collection has been completed for subjects in the study, Unscheduled visits – see [Section 8.6](#)

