## 9 STUDY ASSESSMENTS

A written, signed Informed Consent Form (ICF), and Health Insurance Portability and Accountability Act (HIPAA) authorization is required before any study-related procedures are performed.

Upon provision of the signed ICF, each subject will be assigned a unique SIN. For the duration of the clinical study, the subject will be identified using the SIN in all documentations and discussion.

The planned study assessments are in [Table 3: Schedule of Assessments](#). At each visit, assessments/procedures should be performed in the following order:

1. Investigator assessments (weather assessment first, then proceed to study visit only if suitable, then proceed with assessments including efficacy and safety)
2. Electrocardiogram (ECG) should be done before vital signs measurements (and blood draws). See [Section 9.2.9](#).
3. Sample collections for laboratory assessments at Visits 1 and 6.
4. In selected sites clinical photographs are taken of the treatment areas at Visits 2 and 6.
5. The AKs in the treatment area are counted, mapped, and graded at Visits 2, 4, and 6. The maps from Visits 4 and 6 are compared to the map from Visit 2. For the treatment visits (Visits 2 and 4) steps 5-13 are followed.
6. Sunscreen is applied to the target area by site personnel, subject applies sunscreen to other areas which will be exposed during outdoor daylight exposure.
7. Removal of crusts and scales with a sharp curette of the AK lesions to be treated
8. Application of study drug to AK lesions on face and scalp
9. After 30 minutes, the subject moves outdoors for exposure to daylight.
10. The subject remains outdoors for 2 hours and then comes inside the investigative site.
11. The subject assesses pain on the NRS form at Visit 2 and 4
12. The study drug is washed off after the daylight exposure has been completed.
13. The subject applies sunscreen to the treatment areas and other sun-exposed areas (before leaving the investigative site).
14. The subject fills out the questionnaire at Visits 4 and 6.
15. The Investigator asks the subject the Safety Visit Question at Visits 3 and 5.
16. The Investigator assesses the Subject Skin Aspect Assessment at Visit 6.

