### 9.2.8 Physical Examination

A complete physical examination should be performed at the screening and final visits, according to [Section 8.1.2](#). A complete physical examination will include assessments of the head, ears, eyes, nose, throat, neck (including thyroid), skin/integumentary system, cardiovascular system, respiratory system, gastrointestinal system, musculoskeletal system, lymph nodes, and nervous system.

Investigators should assess all abnormal findings for clinical significance. All CS abnormal findings at the screening visit will be recorded in the medical history form. Any CS changes from the screening visit will be recorded as an AE.

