10.1.2 Missing Dates Management

- Start Date Imputation of Adverse Events:
 - ✓ Imputation of adverse event end date has to be done before imputation of event start date.
 - ✓ Completely missing: Impute to the first study treatment date.
 - ✓ Missing day and month: Impute to January 1st, unless year is the same as year of first study treatment dose then impute to the first study treatment date.
 - ✓ Missing day: Impute to the 1st of the month, unless month and year are the same as month and year of first study treatment dose then impute to the first study treatment date.
 - ✓ If imputed event start date is after event end date (imputed or not), set the event start date to the imputed event end date.

- Start Date Imputation of Prior/Concomitant Therapies and Medical/Surgical Procedures:
 - ✓ Imputation of therapy/procedure end date has to be done before imputation of therapy/procedure start date.
 - ✓ Completely missing: Impute to the first study treatment date.
 - ✓ Missing day and month: Impute to January 1st, unless year is the same as year of first study treatment dose then impute to the first study treatment date.
 - ✓ Missing day: Impute to the 1st of the month, unless month and year are the same as month and year of first study treatment dose then impute to the first study treatment date.
 - ✓ If imputed therapy/procedure start date is after therapy/procedure end date (imputed or not), set the therapy/procedure start date to the imputed therapy/procedure end date.

- Start Date Imputation of Medical History Diseases:
 - ✓ Imputation of disease end date has to be done before imputation of disease start date.
 - ✓ Completely missing: Leave it missing.
 - ✓ Missing day and month: Impute to January 1st.
 - ✓ Missing day: Impute to the 1st of the month.
 - ✓ If imputed disease start date is after disease end date (imputed or not), set the disease start date to the imputed disease end date.

- End Date Imputation of Adverse Events, Prior/Concomitant Therapies and Medical/Surgical Procedures, Medical History Diseases:
 - ✓ Completely missing and flagged as being ongoing: Leave it missing.
 - ✓ Completely missing and not flagged as being ongoing: Impute to the last contact date.
 - ✓ Missing day and month: Impute to December 31st, unless year is the same as last contact date then impute to the last contact date.

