10.7.3 Adverse Events Analysis

All Adverse Events (AEs) will be coded using MedDRA dictionary (version 22.0).

A treatment-emergent adverse event (TEAE) is defined as an adverse event that occurred, or worsened, on or after the date of the first application of study drug.

Statistical Analysis Plan

All treatment-emergent adverse events will be listed in a by-subject listing which will include both the term reported on the eCRF (verbatim term) and the MedDRA System Organ Class and Preferred Term. Relative start and stop days will be included along with the actual onset and resolution dates. Pre-treatment AEs will be listed separately.

If relationship to study drug/procedures is missing the closest relationship, i.e. “Related”, will be imputed. If severity is missing the greatest severity, i.e. “Severe”, will be imputed.

A summary table of TEAEs will be provided for each of the following in the safety population by treatment group and overall:

- Number and percentage (n, %) of subjects with any TEAE and frequency of TEAEs overall and by System Organ Class and Preferred Term;
- Number and percentage (n, %) of subjects with any TEAE and frequency of TEAEs, that occurred in >1% of subjects of the safety population, overall and by System Organ Class and Preferred Term;
- Number and percentage (n, %) of subjects with any AESI and frequency of AESIs overall and by System Organ Class and Preferred Term;
- Number and percentage (n, %) of subjects with any TEAE by closest relationship to study drug and frequency of TEAEs by closest relationship to study drug overall and by System Organ Class and Preferred Term;
- Number and percentage (n, %) of subjects with any TEAE by closest relationship to study procedures and frequency of TEAEs by closest relationship to study procedures overall and by System Organ Class and Preferred Term;
- Number and percentage (n, %) of subjects with any TEAE related to the study drug and frequency of TEAEs related to the study drug by System Organ Class and Preferred Term;
- Number and percentage (n, %) of subjects with any TEAE related to the study procedures and frequency of TEAEs related to the study procedures by System Organ Class and Preferred Term;
- Number and percentage (n, %) of subjects with any TEAE by greatest severity and frequency of TEAEs by greatest severity overall and by System Organ Class and Preferred Term;

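### Every Visit 6 skin-aspect score of 2 or less becomes an adverse event, with no pre-treatment rating of the same site and no new-or-worse condition, so marks already present cannot be reliably separated from treatment effects

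*Protocol*

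**What the plan says.** The rule under Table 9 of the protocol is unconditional: "In the event of the score of 2 or less for the clinical assessment of subject's skin aspect, it will be recorded as an AE". SAP 6.2.3 repeats it. On the 0 to 3 scale this covers Good (2), Fair (1) and Poor (0).

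The rating is made "At Visit 6, for each lesion that has responded completely". The procedure list in Protocol Section 9 agrees: "The Investigator assesses the Subject Skin Aspect Assessment at Visit 6". The only other timing is footnote d of the schedule of assessments, "Should be performed earlier if subject discontinues before Visit 6", which is still after baseline. Neither the protocol schedule (Table 3) nor the SAP schedule (Table 1) has a rating at Screening, Visit 2 or Visit 4.

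On analysis, SAP 10.7.3 ties the definition to the first use of the cream: "A treatment-emergent adverse event (TEAE) is defined as an adverse event that occurred, or worsened, on or after the date of the first application of" [the cream]. For adverse event start dates, SAP 10.1.2 has the rule "Completely missing: Impute to the first study treatment date". Pre-treatment AEs are listed separately (Protocol 10.1.4.2, SAP 10.7.3).

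**The concern.** The trigger is an absolute score at one time point. Table 9 compares redness and pigmentation with adjacent skin, and gives no comparator for scarring, atrophy or induration. It never compares a site with itself before treatment.

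Marks that predate the study are foreseeable. Excision, Mohs' surgery, cryosurgery, peels and dermabrasion are excluded only within 12 weeks of Baseline (Protocol Table 4). Protocol 6.1 itself notes residual scarring after destructive therapies.

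At stake is the local safety profile. Redness, scarring and pigment change are effects that a label for this product would describe. The AEs from this rule feed the TEAE tables by arm, preferred term, relationship and severity, and the lists of common events. If old marks are mixed in, those tables overstate local effects, and may do so unequally between the arms.

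**Working it through.** **1. The rule beside the plan's other AE rules**

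| Assessment | When a finding becomes an AE |
|---|---|
| Laboratory (Protocol 9.2.5) | Clinically significant, and absent at screening or worse since |
| Vital signs (9.2.7) | Clinically significant change from screening |
| Physical examination (9.2.8) | "Any CS changes from the screening visit will be recorded as an AE" |
| ECG (9.2.9) | Clinically significant; no change condition |
| Skin aspect (9.2.3) | Any score of 2 or less; no change condition, no significance threshold |

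The general AE definition (9.2.4) mentions pre-existing conditions only when they are exacerbated. Skin aspect is the one assessment in this table with neither safeguard.

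**2. How an old mark reaches the TEAE tables**

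Take a site with an unchanged pale patch from cryosurgery more than 12 weeks before Baseline. The lesion clears, the pigment difference from adjacent skin is moderate, the score is 2, and an AE is recorded. What follows depends on the onset entered:

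- Full pre-treatment date: not a TEAE.
- Month and year known, day missing: set to the 1st of that earlier month, so not a TEAE.
- Year only, and the same year as first treatment: set to the first treatment date, so a TEAE.
- Completely missing: set to the first treatment date, so a TEAE.
- Date of Visit 6, when it was first rated: a TEAE.

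A site whose redness began after treatment also scores 2 and is recorded identically. No required record at lesion level tells the two apart. The Visit 2 map holds lesion location and grade. The screening skin examination is not by lesion, and only clinically significant findings go to medical history. Photographs are optional, in about 30 subjects (9.3).

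**3. Size**

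The plan states no figure to reproduce, and the documents do not give q, the share of treated sites already carrying a mark that would score 2 or less. The figures below are illustrations. They assume that every such mark is given a post-treatment onset.

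*Independent lesions.* For a subject with k cleared lesions, P(at least one such AE) = 1 − (1 − q)^k.

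| q | k = 4 | k = 8 | k = 12 |
|---|---|---|---|
| 1% | 3.9% | 7.7% | 11.4% |
| 2% | 7.8% | 14.9% | 21.5% |
| 5% | 18.5% | 33.7% | 46.0% |

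*By arm.* From the documents: 4 to 12 lesions, 380 and 190 subjects, complete response 45% and 15%. Assumed: mean 7.2 lesions, and mean lesion clearance 80% (MAL) and 45% (vehicle), that is 7.2 × 0.80 = 5.8 and 7.2 × 0.45 = 3.2 cleared lesions. Averaging the formula over simulated subjects, with clearance calibrated to those response rates, gives:

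| q | MAL | Vehicle |
|---|---|---|
| 1% | 5.6% (21 of 380) | 3.2% (6 of 190) |
| 2% | 10.9% | 6.2% |
| 5% | 24.9% | 14.4% |

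Check at q = 1%: 1 − (1 − 0.01 × 0.80)^7.2 = 5.6% and 1 − (1 − 0.01 × 0.45)^7.2 = 3.2%.

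*Other clearance inputs.* Use 8 lesions, 70.1% clearance for MAL (the European study in Protocol 6.2.1, after one treatment) and an assumed 30% to 50% for vehicle. Then 1 − (1 − q × clearance)^8 gives 5.5% against 2.4% to 3.9% at q = 1%, and 10.7% against 4.7% to 7.7% at q = 2%.

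*Full clustering.* If marks affect all sites of a subject or none, the proportion is simply q among subjects with at least one cleared lesion: about 1% in either arm at q = 1%.

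**The case against.** The strongest reply is that the rule says AE, not TEAE. A reader might infer that every old mark is counted as treatment-emergent. The documents do not support that. The AE form asks for an onset date, the TEAE definition requires onset or worsening on or after first application, pre-treatment AEs are listed separately, and a known earlier month is imputed to before treatment. This stands: entry into the TEAE tables is the default outcome, not a certainty.

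A reader might also infer that skin aspect alone lacks a change rule. ECG lacks one too, although it does require clinical significance.

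A reader might infer that these events alone would fill the list of TEAEs above 1%. That is not shown. The list is by preferred term, and 1% of 570 is 5.7 subjects. The 21 + 6 = 27 subjects in the illustration could be spread over terms for scar, atrophy, induration, redness and pigment change.

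There are partial safeguards. The same investigator rates a subject where possible, pigmented AKs are excluded, redness and pigment change must be at least moderate relative to adjacent skin to lower the score to 2, and causality is judged per event, so an old scar can be rated unrelated. The imputation to related applies only when the relationship is missing. These reduce the problem, but none supplies a pre-treatment reference for the same site.

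Finally, over-reporting is conservative for safety, safety data get summary statistics only, and Table 9 scores are tabulated separately (SAP 10.8.3). This limits the seriousness. It does not make the TEAE tables interpretable for local effects.

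**Conclusion.** The concern holds. Read literally, the rule records unchanged pre-existing marks as AEs, out of line with the general AE definition and with the laboratory, vital-sign and physical-examination rules. Once recorded, they cannot be reliably separated from treatment-emergent effects unless the investigator supplies a pre-treatment onset.

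Randomization does not remove the problem, because the number of rated sites depends on response. If MAL clears more lesions, it has more chances of such an AE even with no effect on skin aspect.

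The size rests on q, which is unknown, on how far marks cluster within subjects, and on the onset dates entered. At q = 1% it ranges from about 1% of subjects with a cleared lesion in either arm (full clustering) to about 5.6% of MAL and 3.2% of vehicle subjects (independent lesions). The gap between arms is largest under independence and mostly disappears under full clustering. Only the safety tables are affected.

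**What to change.** In Protocol 9.2.3 and SAP 6.2.3, state that a score of 2 or less is recorded as an AE only if the finding is new or worse than before the first treatment. Have the investigator note pre-existing scarring, atrophy and pigment change at each treated site on the Visit 2 map. Redness and induration of the keratosis itself are not useful references and need not be noted.

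If data collection is closed, flag in SAP 10.7.3 the AEs that arise only from a skin-aspect score, and present the TEAE tables with and without them.

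In either case keep the planned tabulation of all Table 9 scores, so that no safety information is lost.

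The cost is one sentence in each document and a short note on a map that is already drawn for each subject, or one AE flag and a repeat of the TEAE tables. The downside is that the investigator must judge what is new or worse.

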### 10.1.4.2 Adverse Events

Treatment-emergent AEs, defined as those AEs occurring after the first administration of study treatment until the last study visit, will be tabulated in frequency tables by system organ class and preferred term based on the Medical Dictionary for Regulatory Activities for each study phase. Additional summary tables will be provided for SAEs, AESIs, AEs related to the study drug(s) (defined as the ones with a reasonable possibility of causal relationship with the study drug), AEs related to the study procedures (defined as the ones with a reasonable possibility of causal relationship with the study procedures), and AEs leading to treatment discontinuation and study withdrawal. For a given AE, a subject will be counted once even if he/she has experienced multiple episodes of that particular AE.

Pretreatment AEs will be listed separately.

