## 10.2 Determination of Sample Size

A long-term follow up study is planned to gather data about recurrences at around the 1 year time point after the DL- PDT treatments.

Subjects who achieve a complete response at Visit 6, 12 weeks after the last DL-PDT treatment, will be offered the opportunity to be followed in a 9-month long-term follow-up study to have treated lesions assessed for recurrence. The sample size calculation is based on providing enough subjects to enable the detection of a treatment difference in the primary endpoint and ensuring approximately 100 subjects complete the long-term follow-up study.

Approximately 675 subjects will be screened for a total of 570 subjects to be randomized (380 in the MAL DL-PDT arm and 190 in the vehicle cream DL-PDT arm using a 2:1 randomization ratio) to have approximately 100 subjects complete the long-term follow-up study. This study will have more than 90% power to detect a 30% difference between MAL cream DL-PDT (45% complete response rate) and vehicle cream DL-PDT (15% complete response rate) and with a type I error of 0.00125 assuming 7% subjects will be non-evaluable at 12 weeks after the last DL-PDT for the primary endpoint, 70% of subjects achieving a complete response at 12 weeks after the last DL-PDT will be enrolled in the LT follow-up study and dropout rate of 10% during LT follow-up study.

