10.8.2 Weather Assessment

A listing of all weather assessment data will be provided.

Statistical Analysis Plan**10.8.3 Subject's Skin Aspect Analysis**

Scores of clinical assessment of subject's skin aspect collected at Visit 6/ET will be summarized by treatment group and overall by reporting the number and percentage of subjects (n, %) for each score. For the aim of summary, the worst score among all the assessed lesions of each subject will be taken into account.

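### The rule that turns a low skin-aspect score into an AE applies only to cleared lesions, so part of any MAL excess in local TEAEs could reflect more lesions being scored

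*Protocol*

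**What the plan says.** - **Which lesions are scored.** Protocol 9.2.3 opens "At Visit 6, for each lesion that has responded completely"; SAP 6.2.3 has the same restriction. A footnote to the schedule (Protocol Table 3) adds "Should be performed earlier if subject discontinues before Visit 6", and SAP 10.8.3 accordingly refers to Visit 6/ET. No skin score is scheduled before treatment.
- **What becomes an AE.** Under Table 9, given a "score of 2 or less for the clinical assessment of subject's skin aspect, it will be recorded as an AE in the eCRF". Score 2 is labelled Good: redness or pigment change is moderate, and scarring, atrophy and induration are absent.
- **How these AEs are tabulated.** SAP 10.7.3 defines a TEAE as "an adverse event that occurred, or worsened, on or after the date of the first application of study drug". Its tables (overall, above 1% and 5%, by relationship, by severity, by subgroup) neither flag nor separate events entered because of a skin score.
- **How subjects are counted.** Protocol 10.1.4.2: "For a given AE, a subject will be counted once even if he/she has experienced multiple episodes of that particular AE".
- **How the skin score itself is summarised.** SAP 10.8.3 shows subjects by score, where "the worst score among all the assessed lesions of each subject will be taken into account". It does not ask for the number of lesions scored.

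**The concern.** The trigger for recording an AE depends on an efficacy outcome that the trial is designed to show differs between arms. A cleared lesion is inspected against a numeric scale, and anything short of the top score must go on the AE form. A lesion that has not cleared may show the same redness or pigment change, but no score is given and no entry is forced.

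More cleared lesions mean more chances for at least one forced AE per subject. Even if MAL and vehicle left the skin in the same condition lesion for lesion, the MAL arm could show a higher subject-level rate of local TEAEs. Safety is part of the primary objective (Protocol 7.1), and the plan relies on this study without a second pivotal one (Protocol 10.1.3.1). A reader of the TEAE tables alone could not tell this artefact from real local harm. The TEAE subgroup tables share the problem, because a subject with 9-12 lesions has more lesions that can be scored than one with 4-8.

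**Working it through.** **The plan's own figures.** The documents give no figure for this point. The response rates used below come from the sample-size section, whose figures reproduce. For 45% versus 15% complete response with 380:190 subjects and two-sided alpha 0.00125, power exceeds 99.99%, against a stated figure of more than 90%. Expected MAL completers of long-term follow-up are 380 × 0.93 × 0.45 × 0.70 × 0.90 = 100.2, against a stated figure of about 100.

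**Subjects with every lesion scored, on the plan's rates.** MAL: 380 × 0.93 × 0.45 = 159 of 353. Vehicle: 190 × 0.93 × 0.15 = 26.5 of 177.

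**Inputs for an illustration with no true difference in skin outcome**
- Lesions per subject: k = 8, the middle of the permitted 4 to 12.
- MAL lesion clearance: c = 0.70, from the European study in Protocol 6.2.1 (70.1%, one treatment, PP population).
- Vehicle lesion clearance: not in the documents; assumed 0.30 to 0.60.
- Chance that a scored lesion gets 2 or less: q, not in the documents; assumed 1% to 10% and equal in both arms.
- Uncleared lesions: assumed to yield no AE through the general route.

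**Model A: lesions independent.** P(at least one score-triggered AE) = 1 − (1 − q·c)^k. For q = 10%, MAL is 1 − 0.93^8 = 44.0%, and vehicle at c = 0.30 is 1 − 0.97^8 = 21.6%.

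| q | MAL, c = 0.70 | Vehicle, c = 0.30 | c = 0.40 | c = 0.50 | c = 0.60 | Gap in points | All lesions scored |
|---|---|---|---|---|---|---|---|
| 1% | 5.5% | 2.4% | 3.2% | 3.9% | 4.7% | 3.1 to 0.8 | 7.7% |
| 2% | 10.7% | 4.7% | 6.2% | 7.7% | 9.2% | 6.0 to 1.5 | 14.9% |
| 5% | 24.8% | 11.4% | 14.9% | 18.3% | 21.6% | 13.4 to 3.2 | 33.7% |
| 10% | 44.0% | 21.6% | 27.9% | 33.7% | 39.0% | 22.4 to 5.0 | 57.0% |

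The last column is the rate in both arms if every treated lesion were scored. The gap then vanishes, which shows that it comes from scoring cleared lesions only. With q = 5% and vehicle clearance 0.30, the gap grows with lesion number: 7.4 points at k = 4, 13.4 at k = 8 and 18.2 at k = 12.

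**Model B: skin outcome fully clustered.** Suppose that all scored lesions of a susceptible subject get 2 or less, and none do in other subjects. The rate is then q × P(at least one lesion cleared). For q = 10%:
- MAL: 10% × (1 − 0.3^8) = 10.0%
- Vehicle, c = 0.30: 10% × (1 − 0.7^8) = 9.4%
- Vehicle, c = 0.50: 10% × (1 − 0.5^8) = 10.0%

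The gap is at most 0.6 points.

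**Model C: clearance correlated within subject.** Independent clearance at 70% would give a complete response rate of 0.7^8 = 5.8%, far below the planned 45%, so clearance must be correlated. A beta-binomial model calibrated to 45% and 15% gives P(at least one cleared) = 0.900 on MAL, and 0.474 or 0.850 on vehicle (mean clearance 30% or 50%). At q = 10%:
- Skin outcomes independent: 41.7% versus 18.4% or 31.5%, a gap of 23.3 or 10.2 points.
- Skin outcomes fully clustered: 9.0% versus 4.7% or 8.5%, a gap of 4.3 or 0.5 points.

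**The case against.** The strongest case against is that AE capture does not depend on the skin score. Every medical event that the investigator observes is to be recorded (Protocol 9.2.4). The treatment area is examined at each visit (9.2.4.2). At Visit 6 each treated lesion is identified again, graded and judged by sight and touch (9.1.1), and the final physical examination includes the skin (9.2.8). Uncleared lesions are therefore inspected and their signs are reportable. This stands, and it limits the point: what differs is a numeric threshold with compulsory entry. It does not remove the point, because none of these routes makes moderate redness or pigment change an automatic AE. In the physical examination only clinically significant changes qualify.

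The objection to the size also stands. Vehicle clearance and q are assumed, and clustering shrinks the gap sharply. Protocol 6.3 reports that signs of phototoxicity after conventional PDT mostly lasted 1 to 2 weeks, while scoring is at 12 weeks and slight redness still scores 3; q may be small. Counting every triggered event as one that would otherwise go unrecorded also overstates the artefact.

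A reader might infer more than the documents support:
- **That AE ascertainment starts at Visit 6.** AEs are collected from consent at every visit, with a sensitization question at Visits 3 and 5 and a rule for pain needing intervention.
- **That TEAE rates are not comparable between visits.** SAP 10.7.3 plans no by-visit TEAE table.
- **That pre-existing pigment change necessarily counts as a new event.** It might, since Table 9 compares with adjacent skin and there is no earlier score. But onset dates are recorded, a TEAE must be new or worse after first application, and pigmented AKs are excluded.
- **That all these events enter the related tables.** Only those judged related do, or those with the relationship missing.

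**Conclusion.** The concern holds in limited form. A compulsory AE trigger is tied to lesion clearance, and the TEAE tables do not separate the events that it generates. The direction, a higher apparent rate of local TEAEs on MAL, follows on two conditions: MAL clears more lesions, and the risk per scored lesion is equal in both arms. The planned response rates of 45% and 15% make the first condition likely; the second is the no-difference case.

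The size is unknown. With 8 lesions it runs from under 1 point (skin outcome fully clustered within subject) to 22.4 points (independent lesions, q = 10%, vehicle clearance 30%), or 23.3 with correlated clearance. These are illustrations, not estimates or bounds.

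The consequence is modest. Safety analyses are descriptive (SAP 10.7), the bias works against MAL, and the efficacy analysis is untouched. By-subject listings and the skin-score summary would let a careful reader trace many of these events. This is a cheap improvement in presentation, not a threat to the trial's conclusions.

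**What to change.** Leave the site procedures, the AE rule and the full TEAE tables as they are, and make two additions to the SAP.

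1. **SAP 10.7.3:** add supplementary versions of the overall, related and SOC/PT TEAE tables that leave out AEs matching a skin-aspect score of 2 or less. Fix the matching rule (AE term and onset date) at the blind review.
2. **SAP 10.8.3:** report by arm the number of subjects and lesions scored, and the proportion of scored lesions at each score. Take these from the lesion-level skin-score data; the AE fields listed in Protocol 9.2.4 include no lesion identifier.

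The cost is a few extra tables and one derived flag. No AE field records why an event was entered, so some matches will be ambiguous, for example redness with an earlier onset. The supplementary tables also drop true scarring or atrophy, so they must be read beside the full ones. The proportion per scored lesion removes the effect of unequal lesion numbers, but it still describes cleared lesions only and is not a randomized comparison; a footnote should say so.
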